# 4.4 Missing and Partial Data

In general, other than for partial dates, missing data will not be imputed and will be treated as missing. The algorithms for imputation of partial dates vary depending upon the parameter. These are presented in Appendix A.

#### 4.5 Safety Observation Period

The safety observation period is defined as time from first dose date of study treatment to the earlier of the date of the decision to permanently discontinue study treatment+ 30 days or date subject withdrew consent or date of death or data cut-off date.

Generally only the safety data (including adverse events, laboratory results, vital signs, ECG, ECOG PS, concomitant medications and etc.) reported during the safety observation period will be analyzed and summarized, unless otherwise specified in this plan.

# 4.6 Definition of Prior, Concomitant, and Subsequent Therapy

For the purpose of inclusion in summary tables, incomplete medication or radiation start and stop dates will be imputed as detailed in Appendix A. Based on imputed start and stop dates:

- Prior medications/radiation therapies are defined as medications with a start date occurring before the date of first dose of study treatment.
- Concomitant medications/radiation therapies are defined as medications that stop or continue on or after date of first dose day through the end of safety observation period.
- Subsequent medications/radiation therapies are defined as those that stop or continue on or after the date of randomization.
- Medications/radiation therapies may be summarized as prior, concomitant and/or subsequent.

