#### **4.3 Exclusion Criteria**

1. Fibrolamellar carcinoma or mixed hepatocellular cholangiocarcinoma
2. Receipt of more than 2 prior systemic therapies for advanced HCC. Additional prior systemic therapies used as adjuvant or local therapy are allowed.
3. Any type of anticancer agent (including investigational) within 2 weeks before randomization
4. Radiation therapy (eg, I-131 or Y-90) within 4 weeks (2 weeks for radiation for bone metastases) or radionuclide treatment within 6 weeks of randomization (subject is excluded if there are any clinically relevant ongoing complications from prior radiation therapy)
5. Prior cabozantinib treatment
6. Known brain metastases or cranial epidural disease unless adequately treated with radiotherapy and/or surgery (including radiosurgery) and stable for at least 3 months before randomization. Eligible subjects must be without corticosteroid treatment at the time of randomization.
7. Concomitant anticoagulation, *at therapeutic doses*, with anticoagulants such as warfarin or warfarin-related agents, low molecular weight heparin (LMWH), thrombin or coagulation factor X (FXa) inhibitors, or antiplatelet agents (eg, clopidogrel). Low dose aspirin for cardioprotection (per local applicable guidelines), low-dose warfarin ( $\leq$  1 mg/day), and low-dose LMWH are permitted.
8. The subject has uncontrolled, significant intercurrent or recent illness including, but not limited to, the following conditions:

- a. Cardiovascular disorders including
  - i. Symptomatic congestive heart failure, unstable angina pectoris, or serious cardiac arrhythmias
  - ii. Uncontrolled hypertension defined as sustained BP > 150 mm Hg systolic, or > 100 mm Hg diastolic despite optimal antihypertensive treatment
  - iii. Stroke (including TIA), myocardial infarction, or other ischemic event within 6 months before randomization
  - iv. Thromboembolic event within 3 months before randomization. Subjects with thromboses of portal/hepatic vasculature attributed to underlying liver disease and/or liver tumor are eligible
- b. Gastrointestinal (GI) disorders including those associated with a high risk of perforation or fistula formation:
  - i. Tumors invading the GI tract, active peptic ulcer disease, inflammatory bowel disease (eg, Crohn's disease), diverticulitis, cholecystitis, symptomatic cholangitis or appendicitis, acute pancreatitis or acute obstruction of the pancreatic duct or common bile duct, or gastric outlet obstruction

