# 6.6 Non-Protocol Anti-cancer Therapy

For the purpose of supporting safety evaluation:

Non-radiation concomitant (see definition in section 4.6.) NPACT will be summarized by ATC text and WHO Drug base substance preferred name in the Safety population.

For the purpose of supporting efficacy evaluation:

All subsequent (see definition in section 4.6.) NPACT, including radiation therapy, will be summarized by treatment group in the ITT population as follows:

- Based on the non-radiation therapy received subjects will be categorized into one or more of the following categories: systemic, local, or unknown and all NPACTs falling under these categories will be summarized by ATC text and WHO Drug based substance preferred name
- Time to first systemic NPACT will be summarized by descriptive statistics
- Frequency counts and percentages will be presented for radiation therapy indication, type and site

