# 7.2.1 Progression-Free Survival (PFS)

#### 7.2.1.1 Definition

Duration of PFS is defined as the time from randomization to the earlier of the date of radiographic progression or date of death due to any cause.

PFS (months) =(earliest date of progression, death, censoring – date of randomization + 1)/30.4375

The primary analysis of PFS will include all subjects in the ITT population and will include radiographic progression events as determined by the investigator per RECIST 1.1 and deaths.

The recorded date of radiographic progression is the date of the tumor assessment visit at which progression is declared. If multiple scan dates are associated with a tumor assessment visit, the earliest assessment date within the set will be chosen as the progression date.

Only adequate tumor assessments (ATAs) will be considered in the determination of radiographic progression and censoring dates. For the purpose of this study, ATA is defined as one that results in a time point assignment of: response (complete or partial), stable disease/(non-CR, non-PD), or progression. For PFS, ATA is based on soft tissue evaluation by CT/MRI and/or new lesions identified by bone scan.

General censoring rules for the primary analysis of PFS are described below:

• Subjects who receive systemic or liver directed local NPACT or non-protocol radiation therapy (other than to bone) or surgery to resect tumor lesions before experiencing an

event will be right censored at the date of the last ATA on or prior to the date of initiation of subsequent therapy/surgery. If there is no such tumor assessment after randomization, the subject will be right censored on the date of randomization.

- Subjects who have not experienced an event (and are not otherwise censored) at the time of data cutoff will be right censored on the date of their last tumor assessment after randomization that is on or prior to the data cutoff. If there is no such tumor assessment after randomization, the subject will be right censored on the date of randomization.
- Subjects who miss two or more ATAs (operationally defined as 126 days without an ATA) followed by an event (progression or death) will be right censored on the date of their most-recent ATA prior to the missing assessments. If there is no such tumor assessment after randomization, the subject will be right censored on the date of randomization

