#### **Incomplete Concomitant Medication End Date**

If *year* is missing (or completely missing): do not impute.

If (year is present and month and day are missing) or (year and day are present and month is missing):

Set month and day to December 31st.

If year and month are present and day is missing:

Set day to last day of the month.

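### SAP 4.6 defines subsequent therapy by its stop date, so SAP 6.6 can count anticancer therapy begun before randomization as post-randomization NPACT, and the PFS rules leave room for the same error

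*SAP*

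**What the plan says.** SAP 4.6 sorts therapies into prior, concomitant and subsequent. Prior is set by the start date (before first dose). Subsequent is set by the stop date: "Subsequent medications/radiation therapies are defined as those that stop or continue on or after the date of randomization". One record may fall in several classes: "Medications/radiation therapies may be summarized as prior, concomitant and/or subsequent". The classes use imputed dates: "For the purpose of inclusion in summary tables, incomplete medication or radiation start and stop dates will be imputed as detailed in Appendix A".

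Appendix A has one end-date rule for non-study therapy, titled for concomitant medication. With only the day missing: "Set day to last day of the month". With the month missing: "Set month and day to December 31st".

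SAP 6.6, in the part that supports the efficacy evaluation, cites 4.6 for subsequent therapy: "NPACT, including radiation therapy, will be summarized by treatment group in the ITT population as follows". The list that follows includes time to first systemic NPACT.

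The primary PFS rule in SAP 7.2.1.1 censors subjects who receive NPACT before an event at the last adequate tumor assessment (ATA) on or before initiation of the subsequent therapy. The fallback is: "If there is no such tumor assessment after randomization, the subject will be right censored on the date of randomization". Table 3 also speaks of subsequent NPACT. Neither place defines the word or cites 4.6.

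The washout for anticancer agents is short. Protocol 4.3 excludes: "Any type of anticancer agent (including investigational) within 2 weeks before randomization".

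**The concern.** In an efficacy analysis, subsequent therapy should mean therapy started after randomization. A stop-date definition also takes in therapy that began earlier and merely ends, or appears to end, after randomization. Both Appendix A end-date rules move dates as late as possible, which pushes incomplete records towards the subsequent class.

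The direct effect is on the NPACT tables in SAP 6.6. They are the tables from which a reader judges how much post-randomization treatment could have influenced OS. Prior sorafenib in those tables would mislead.

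The possible further effect is on PFS and objective response rate (ORR), which are formally tested at 0.04 and 0.01 once OS succeeds. Their censoring rules should not depend on how a programmer reads an undefined word.

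**Working it through.** The documents give no figure on this point, so there is none to reproduce. The check applies the date rules literally to one hypothetical record and then asks whether the washout rules such a record out.

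**Hypothetical record.** Prior therapy started 1 Sep 2014 and truly stopped 2 Mar 2015, with the end date recorded only as March 2015. Randomization was on 20 Mar 2015. The gap is 18 days, so the 2-week washout is met.

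1. Appendix A end date, day missing: 31 Mar 2015.
2. SAP 4.6: 31 Mar is on or after 20 Mar, so the record is subsequent. By its true stop date (2 Mar) it is not. By its start date it is not.
3. SAP 6.6: the record enters the subsequent NPACT tables. Counted from randomization with the SAP 4.2 convention, its start is day −200 (1 Sep 2014 minus 20 Mar 2015), so time to first NPACT is negative.

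**If the same flag were carried into PFS and response:**

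4. Primary PFS (PFS1): no post-randomization ATA lies on or before 1 Sep 2014, so the fallback applies. PFS = (0 + 1)/30.4375 = 0.033 months, censored.
5. PFS2, where NPACT is an event on its own date: (−200 + 1)/30.4375 = −6.5 months.
6. Best overall response (SAP 7.2.2.1) counts only assessments before a PFS censoring event, so all later responses are excluded.

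**Does the washout prevent this?** Take randomization dates uniform over a 365-day year (an assumption). A stop g days earlier falls in the same calendar month for a share Σ max(0, L − g)/365, where L is the length of each month. It falls in the same calendar year for a share (365 − g)/365.

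| Gap g (days) | Same month |
|---|---|
| 14 | (365 − 12×14)/365 = 197/365 = 54% |
| 21 | (365 − 12×21)/365 = 113/365 = 31% |
| 28 | (365 − 12×28)/365 = 29/365 = 8% |
| 30 | 7/365 = 2% |

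With the month also missing, the end date becomes 31 December. A stop 14 days earlier is then flagged for 351/365 = 96% of randomization dates, and a stop 42 days earlier for 323/365 = 88%.

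The washout therefore does not exclude the case. These shares apply only to records with an incomplete end date, and the documents do not say how common those are. Therapy that truly overlaps randomization is flagged without any imputation.

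**The case against.** The strongest counter-argument concerns PFS. SAP 4.6 introduces its imputed dates for inclusion in summary tables. SAP 7.2.1.1 does not cite it, is keyed to initiation of the therapy, and measures an endpoint that starts at randomization, so its natural reading is therapy begun afterwards. Appendix A refers to a Subsequent Anti-Cancer Therapy CRF, and SAP 7.6 refers to a separate history CRF for prior therapy. A negative event time is absurd enough to suggest that nobody intends it. All of this stands. A reader might infer that the SAP as written censors PFS on day 1 for these subjects; it does not say so. A reader might also infer that the exploratory OS analysis is affected, but SAP 7.1.4 limits that censoring to therapy received after randomization.

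Two further points limit the size. Applying the concomitant-medication rule to history-CRF records is an inference, since Appendix A has no end-date rule for prior anticancer therapy. And a site usually needs the exact stop day to confirm the 2-week washout when therapy ended in the month of randomization, so the day is least likely to be missing where it matters. Misclassification would also rest on pre-randomization dates and should be balanced between arms.

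None of this removes the problem in SAP 6.6. That section cites 4.6 by name and does not restrict itself to the Subsequent Anti-Cancer Therapy CRF. Nor does it settle the PFS wording: 4.6 is the SAP's only definition of subsequent, and 7.2.1.1 lacks the limit to therapy after randomization that 7.1.4 states.

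**Conclusion.** The point holds for the SAP 6.6 tables. Followed as written, the definition counts therapy begun before randomization as subsequent NPACT when it overlaps randomization, or when an incomplete end date is moved forward, provided the concomitant-medication end-date rule is applied to it. The result is overstated post-randomization therapy and possibly a negative time to first NPACT.

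For PFS1, PFS2 and best overall response the consequence is conditional on the 4.6 flag being reused there. That is an ambiguity to close, not a stated error. The primary OS analysis is untouched.

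No count of affected subjects can be given. It is tempting to combine an assumed 5–10% of end dates lacking the day with an assumed stop 14–30 or 14–60 days before randomization (same-month shares 27.8% and 10.0%). That would give between 760 × 0.10 × 0.05 ≈ 4 and 760 × 0.278 × 0.10 ≈ 21 subjects. The documents support neither the missing-day rate nor the gaps, so this range should not be quoted as the size of the problem.

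**What to change.** - **SAP 4.6:** define subsequent anticancer and radiation therapy as therapy with a start date on or after randomization.
- **SAP 6.6, 7.2.1.1, Table 3 and 7.2.2:** cite that definition.
- **Appendix A:** cap imputed end dates of records from the prior-therapy CRFs at the day before randomization, unless the record is marked as ongoing.
- **Therapy truly ongoing at randomization:** list it separately as a washout deviation.

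The last item covers the one real cost. Under a start-date definition, such therapy leaves the subsequent class and would otherwise drop out of the ITT tables. Non-radiation therapy that continues past first dose would still appear as concomitant NPACT in the Safety population under SAP 6.6.

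Otherwise the change is a few sentences and needs no new data. SAP 4.8 already provides for a revised plan or an addendum approved before unblinding.

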#### 4.7 Software

All analyses will be conducted using SAS Version 9.1 or higher.

# 4.8 Changes to Planned Analyses

Substantive changes to the analyses described in the protocol or in approved versions of this plan will be fully documented in a revised version of the plan approved by the Sponsor prior to unblinding the study to conduct the analyses.

Clarifications, minor corrections, and operational considerations necessary to accurately conduct the analyses that do not materially change the nature of the analysis will be documented in an addendum to this plan that will be also be approved by the Sponsor prior to unblinding the study to conduct the analyses.

#### 5 STUDY POPULATION SUMMARIES

#### 5.1 Enrollment

Subjects are defined to be enrolled at randomization. Enrollment will be summarized by region, country, site and protocol amendments.

# 5.2 Disposition

Subject disposition will be summarized categorically and will include the number and percentage of subjects in the ITT and Safety populations.

The reasons for study treatment discontinuation and study follow-up discontinuation will also be summarized categorically.

# 5.3 Demographic and Baseline Characteristics

Summaries of demographics, stratification factors and baseline characteristics will be presented for subjects in the ITT and Safety populations.

- [A] The demographic characteristics include:
  - Age (continuous)
  - Age category 1
    - < 65 years
    - $\geq$  65 years
  - o Age category 2
    - < 75 years
    - >=75 years

- o Age category 3
  - <65 years
  - 65 to <75 years
  - 75 to <85 years
  - $\geq$ 85 years
- o Sex
  - Male
  - Female
  - Not reported
- o Ethnicity
  - Hispanic or Latino
  - Not Hispanic or Latino
  - Not Reported
- o Race
  - American Indian or Alaska Native
  - Asian
  - Black or African American
  - Native Hawaiian or Other Pacific Islander
  - White
  - Not Reported
  - Other
- o Geographic Region
  - Australia/New Zealand
  - Asia (excluding Japan)
  - Europe
  - North America (Canada/USA)
- → Japanese decent (world-wide)
  - Japanese descent
  - Non-Japanese descent
  - Both Japanese and Non-Japanese descent
  - Not Reported

Note for this study birth date is not collected but age in years is collected at informed consent.

- [B] Categorical summaries of the following stratification factors will be presented as recorded (a) in the IxRS during randomization (b) on the CRF (c) cross tabulation of all 3 stratification factors per IxRS (d) cross tabulation of all 3 stratification factors per CRF (e) cross-tabulation of geographic region and etiology of disease per CRF:
  - etiology of disease
    - HBV [with or without HCV]
    - HCV [without HBV]
    - Other
  - o geographic region (Asia, Other Regions)
  - presence of extrahepatic spread of disease and/or macrovascular invasion (Yes, No)
- [C] Baseline characteristics include:
  - Height in inches
     – descriptive statistics
  - Weight in kg descriptive statistics
  - Body mass index (BMI) in kg/meter, calculated as (weight in kg\*1000)/(Height in cm) –descriptive summary:
  - o ECOG PS: 0, 1, Missing
  - Smoking history
    - Current
    - Former
    - Never
  - Alcohol use Categorical summary for subjects classified as current user, former user or never will be presented
- [D] Descriptive statistics and or categorical summaries for the following baseline laboratory characteristics:
  - o Alpha fetoprotein [AFP] ( $< 400 \text{ ng/ml}, \ge 400 \text{ ng/ml}$ )
  - o Prothrombin International normalized ratio [INR] ( $\leq 2.3, >2.3$ )
  - o Albumin ( $< 35 \text{ g/L}, \ge 35 \text{ g/L}$ )
  - o Total bilirubin in umol/L ( $< 22.23, \ge 22.23 29.07, \ge 29.07$ )
  - o Neutrophil/Lymphocyte ratio ( $< 3, \ge 3$ )

- Albumin and total bilirubin (ALBI) grade derived from calculated ALBI score = [log(Bilirubin in umol/L)\*0.66 (Albumin in g/L)\*0.085]
  - Grade 1: ALBI score  $\leq$  -2.60
  - Grade 2:  $-2.60 < ALBI score \le -1.39$
  - Grade 3: ALBI score > -1.39

For laboratory parameters summarized as baseline characteristics, the most-recent non-missing central or local sample available before the date and time of randomization will be employed. This differs from definition of baseline laboratory values used in safety summaries.

# 5.4 Medical History

General medical history data will be coded per MedDRA.

## 5.5 Cancer History and Current Disease Status

Cancer history and current disease characteristics data collected on the cancer history CRF will be summarized categorically or with descriptive statistics as appropriate. The following summaries are planned:

- Diagnosis of carcinoma of HCC by histology or cytology (Yes, No)
- Current etiology:
  - o Hepatitis B virus (without HCV)
  - o Hepatitis C virus (without HBV)
  - o Hepatitis B and C virus
  - o Hepatitis B virus (regardless of HCV)
  - Hepatitis C virus(regardless of HBV)
  - Alcoholism
  - Nonalcoholic Steatohepatitis (NASH)
  - Other
- Hepatitis B virus surface antigen (HBsAg), Hepatitis B virus core antibody (HBCAB) and HCV laboratory results summary
  - $\circ$  HBsAg(+), HBCAB(+)
  - $\circ$  HBsAg(+), HBCAB(-)
  - $\circ$  HBsAg(-), HBCAB(+)
  - HBsAg(-) , HBCAB(-)

- HCV(+)
- $\circ$  HCV(-)
- Child-Pugh Grade
  - o A (score 5 6)
  - $\circ$  B (score 7 9)
  - $\circ$  C (score 10-15)
- Hepatic Encephalopathy
  - o None
  - o Grade I-II
  - o Grade III-IV
  - Missing or unknown
- Ascites
  - Absent
  - o Slight
  - Moderate
  - Missing or unknown
- Time in years to randomization since diagnosis of HCC as identified by histology or cytology (Note: Incomplete diagnosis dates will be imputed as detailed in Appendix A)
- Currently has locally advanced disease (Yes, No, Unknown)
- Currently has metastatic disease (Yes, No)
- Extent of disease at baseline per target/non-target sites identified by the investigator on the tumor assessment CRFs (liver, lymph node, brain, bone, other, peritoneum, visceral sites other than liver, etc.)
- Number of target/non-target sites at baseline identified on tumor assessment CRFs per investigator  $(1, 2, \ge 3)$
- Has bone metastasis at baseline per history of bone lesion CRF or as identified by target and non-target lesion CRFs (Yes, No)
- Has measurable disease at baseline identified by the investigator on tumor assessment CRFs (Yes, No)
- Current Extent of HCC Disease :
  - o Portal Vein Invasion (Yes, No, Unknown)
  - o Bile Duct Invasion (Yes, No, Unknown)
  - o Macrovascular Invasion (Yes, No, Unknown)

- o Extrahepatic Spread (Yes, No, Unknown)
- o Other (Yes, No)
- MET immunohistochemistry status (High, Low/Negative, Unknown). The status of high and low/negative will be based on cutoff of ≥50% of tumor tissue stained with an intensity of 2+ or 3+). The cut-off is based on historical NSCLC and HCC data, may be adjusted if warranted based on results in initial XL184-309 data transfers
- VEGF-A amplification in circulating tumor cells (Yes, No, Unknown)

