### **BIOMARKERS**

---

Assessment of biomarkers in plasma by multiplexed array will be performed. Serum bone biomarkers will also be assessed. In addition, circulating tumor cells (CTCs) may be analyzed in blood samples collected at selected sites. Samples for these assessments will be collected according to the schedule in Appendix A.

In addition, tumor tissue (archival or recently biopsied) will be obtained at enrollment whenever available for exploratory analysis of MET and potentially other pathway components or modulators associated with the mechanism of action of cabozantinib, as predictive biomarkers.

Collection of these samples may be halted early or sampling frequency may be reduced at the discretion of the Sponsor. If the study transitions to the Open-Label Phase or to the Maintenance Phase, biomarkers will no longer be collected.

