#### **5.7.11 Pharmacogenetics and Biomarkers**

Unless prohibited by local regulations, failure to grant informed consent for this purpose, or sponsor decision, a blood sample will be collected pre-dose on Day 1 of Week 1 for genotyping/single nucleotide polymorphism/copy number variation analysis to correlate genetic variation with PK, safety, tolerability of and response to study treatment.

Assessment of biomarkers in plasma by multiplexed array will be performed. These may include target receptors and ligands (eg, VEGF-A, HGF, soluble VEGFR2, and MET) and other markers related to cabozantinib mechanism of action and/or HCC. Serum bone biomarkers will also be assessed. In addition, CTCs may be analyzed in blood samples collected at selected sites. Samples for these studies will be collected according to the schedule in Appendix A.

In addition, tumor tissue (archival or recently biopsied) will be obtained at enrollment whenever available for exploratory analysis of MET and potentially other pathway components or modulators associated with the mechanism of action of cabozantinib, as predictive biomarkers. Formalin-fixed paraffin embedded (FFPE) tumor blocks are preferred but in cases where this is not possible, 10 unstained freshly-cut FFPE slides should be obtained.

Detailed instructions for sample preparation and shipping will be provided in a separate manual.

Collection of these samples may be halted early or sampling frequency may be reduced at the discretion of the Sponsor.

If the study transitions to the Open-Label Phase or to the Maintenance Phase, biomarker assessments will be discontinued.

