## 7.3 Control of Type I Error

The multiplicity issue resulting from analysis of one primary endpoint (OS), two secondary efficacy endpoints (PFS and ORR), and planning two interim analyses for testing OS will be addressed by employing a fixed-sequence testing procedure, applying a modified Bonferroni procedure (dividing the alpha between the secondary endpoints), and implementing an alpha-spending function.

Up to three event-driven analyses of OS are planned: two interim analyses and a final analysis (see details in section 7.1.3). Inflation of Type 1 error associated with interim analyses will be controlled using a Lan-DeMets O'Brien-Fleming alpha-spending function.

Interim analysis of PFS and ORR are not planned. The testing of these two secondary endpoints will occur only if the result of either an interim analysis or the final analysis of OS achieves statistical significance. The hypothesis for PFS and ORR will be tested in parallel. PFS will be tested at the 2-sided  $\alpha$ =0.04 level of significance and ORR will be tested at the 2-sided  $\alpha$ =0.01 level of significance.

All other statistical evaluations of efficacy will be considered exploratory.

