# 7.6 Subgroups

The following subgroups based on baseline characteristics and stratification factors will be explored for primary and secondary efficacy endpoints

- Age category
  - o <65 years
  - $\circ$  65 to <75 years
  - o 75 to <85 years
  - $\circ$   $\geq$ 85 years
- o Sex

- Male
- Female
- o Race
  - Asian
  - Black or African American
  - White
  - Rest of the races reported/Not Reported
- o Geographic Regions 1
  - Asia (excluding Japan)
  - Europe/Australia/New Zealand
  - North America (Canada/USA)
  - Other
- o Geographic Regions 2
  - Asia
  - Other Region
- o ECOG Performance status at baseline:
  - **-** (
  - 1
  - Missing
- Etiology of disease per stratification factors per IxRS:
  - HBV [with or without HCV]
  - HCV [without HBV]
  - Other
- o Current etiology of disease (per cancer history CRF):
  - HBV [without HCV] (Yes/No/Unk)
  - HCV [without HBV] (Yes/No/Unk)
  - HBV and HCV (Yes/No/Unk)
  - Alcoholism (Yes/No/Unk)
  - Nonalcoholic Steatohepatitis (NASH) (Yes/No/Unk)
  - Other (Yes/No/Unk)
- o Presence of extrahepatic spread of disease and/or macrovascular invasion (per IxRS):
  - Yes
  - No
- Presence of extrahepatic spread of disease and/or macrovascular invasion (per cancer history CRF):
  - Yes

- No
- Visceral sites other than liver, bone, bone+visceral sites other than liver per tumor assessment CRFs per investigator. Visceral sites other than liver will include lung kidney, pancreas and other sites based upon a manual review of the reported sites after all data has been entered in the database
- o Prior systemic non-radiation anti-cancer therapy regimens for advanced HCC per subject per history of non-radiation anti-cancer therapy CRF (1 vs  $\geq$  2)
- Prior receipt of PD-1/PD-L1 per history of non-radiation anti-cancer therapy CRF (Yes, No)
- Prior receipt of Regorafenib per history of non-radiation anti-cancer therapy CRF (Yes, No)
- Prior receipt of Lenvatinib per history of non-radiation anti-cancer therapy CRF (Yes, No)
- Prior receipt of Tivantinib per history of non-radiation anti-cancer therapy CRF (Yes. No)
- Prior receipt of Ramucirumab per history of non-radiation anti-cancer therapy CRF (Yes. No)
- o VEGF-A amplification in circulating tumor cells (Yes, No, Unknown)
- AFP (<400 ng/mL,  $\ge 400 \text{ ng/L}$ ) at baseline
- o Tumor MET status
  - High
  - Low or Negative
  - Unknown

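### Tumor MET is collected to explore whether it predicts cabozantinib benefit, but the SAP uses it for efficacy only as a High versus Low/Negative split, which keeps about 0.5 to 0.8 of the interaction information if benefit changes smoothly with staining

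*SAP*

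**What the plan says.** - **Purpose.** The protocol synopsis (Biomarkers) plans "exploratory analysis of MET and potentially other pathway components or modulators associated with the mechanism of action of cabozantinib, as predictive biomarkers". Protocol 5.7.11 repeats this and makes collection conditional: "tumor tissue (archival or recently biopsied) will be obtained at enrollment whenever available". The relationship of biomarkers to treatment and outcome is a listed additional endpoint in Protocol 2.2 and SAP 2.3.3.
- **Coding.** SAP 5.5 lists "MET immunohistochemistry status (High, Low/Negative, Unknown") and defines High and Low/Negative "based on cutoff of ≥50% of tumor tissue stained with an intensity of 2+ or 3"+. It attributes the cut to earlier lung cancer and HCC data and says that it "may be adjusted if warranted based on results in initial XL184-309 data transfers".
- **Use.** SAP 7.6 lists tumor MET (High, Low or Negative, Unknown) among many subgroup variables: "The following subgroups based on baseline characteristics and stratification factors will be explored for primary and secondary efficacy endpoints". SAP 2.3.3 points to section 7.5 for biomarkers, but 7.5 contains no MET analysis.
- **Status.** SAP 7.3: "All other statistical evaluations of efficacy will be considered exploratory".
- **Other hooks.** Protocol 9.2.3 and 9.3.1 allow exploratory Cox models for baseline and other variables, without saying how MET enters them. SAP 4.8 requires changes to planned analyses to be documented and approved before the study is unblinded.

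**The concern.** Whether a marker is predictive is a question about treatment-by-marker interaction. The cut is applied to a percentage, so the underlying measure runs from 0 to 100. Grouping it at 50% treats staining of 51% and 100% as alike, and 49% as unlike 51%. If benefit rises gradually with staining, that discards information on the one question for which the tissue is collected. Information is scarce to begin with: tissue comes only from subjects who have it, so fewer than all 621 deaths may have a known MET status, and interactions need many more events than main effects.

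The adjustable cut is a second, smaller matter. SAP 5.5 does not say what would warrant a change or which results may inform it. Without that, a reader of the subgroup hazard ratios cannot tell whether the boundary was chosen independently of outcome.

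**Working it through.** **1. The plan's own figure.** Inputs from SAP 2.4: HR 0.76, 2:1 allocation, two-sided 5%, 90% power, 621 deaths. Schoenfeld: D = (1.960 + 1.282)² / [(2/3)(1/3)(ln 0.76)²] = 628, against 621 stated. With Lan-DeMets O'Brien-Fleming looks at 311, 466 and 621 deaths, critical p-values are 0.0031, 0.0184 and 0.0440 (stated 0.0031, 0.0183, 0.044) and power is 89.2%. The OS design reproduces. The documents state no power for any MET analysis.

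**2. Information kept by the split.** If the log hazard ratio is linear in staining, the two-group interaction test keeps r² of the information, where r is the correlation between the score and the High indicator. For a normal score with share High q, r² = φ(z_q)² / [q(1−q)]. The distribution is not in the documents, so several are assumed:

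| Assumed score | Share High | Information kept |
|---|---|---|
| U-shaped, beta(0.5, 0.5) | 50% | 0.81 |
| Uniform | 50% | 0.75 |
| Normal, cut at median | 50% | 0.64 |
| Normal | 30% | 0.58 |
| Normal | 20% | 0.49 |

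**3. Power in this trial.** Further assumptions: MET known for 30%, 50% or 80% of the 621 deaths; two-sided 5%; half High; HR in High versus Low of 0.60 versus 0.95, or 0.65 versus 0.90. The log-averages are √(0.60 × 0.95) = 0.755 and √(0.65 × 0.90) = 0.765, both near the design 0.76.

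For the split, z = |ln(HR_High/HR_Low)| × √[D × 2/9 × q(1−q)]. For the percentage, z is divided by √r². Power = Φ(z − 1.96).

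Example at 50% known and 0.60 versus 0.95: D = 310.5; z = 0.4595 × √(310.5 × 2/9 × 0.25) = 1.91, power 48%. Percentage, normal score: 1.91/√0.637 = 2.39, power 67%.

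| MET known | 0.60 vs 0.95: split, percentage | 0.65 vs 0.90: split, percentage |
|---|---|---|
| 30% | 32%, 46% (14 points) | 18%, 26% (8) |
| 50% | 48%, 67% (19) | 27%, 40% (12) |
| 80% | 67%, 86% (18) | 40%, 57% (17) |

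So the range is about 8 to 19 points for a normal score. The same six cells give about 5 to 12 points for a uniform score and about 3 to 9 for a U-shaped one.

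**4. When the effect is a step.** If benefit jumps exactly at the cut, the split is the correct model and a linear term is the weaker test. With the split at 80% power, the percentage loses about 9 points (U-shaped), 12 (uniform) and 33 (a right-skewed beta(2,5) score with 11% High).

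**The case against.** The strongest reply is that no planned test loses power. MET is one of many subgroups to be explored, with no alpha, interaction test or power target, and the protocol's exploratory Cox provisions leave room for a continuous MET term. That stands. It makes this an improvement to an exploratory analysis and not a defect in the trial's inference. It does not supply the missing analysis, because neither document commits to one.

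A reader might infer that the plan forfeits as much as 30 points of power. The documents do not support this. That value needs a normal score, 20% High, HR 0.60 versus 0.95 and MET known for 80% of deaths (49% versus 79%). The implied overall HR is exp(0.2 ln 0.60 + 0.8 ln 0.95) = 0.87, against the design 0.76 and the 0.84 needed for significance at the final analysis. Power for OS itself would then be only about 37%. Normality is also doubtful: a category named Low/Negative suggests many scores at or near zero.

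A reader might also infer that moving the cut biases the subgroup results. That is not established. SAP 5.5 does not say that the transfers contain arm or outcome data, the sponsor is blinded, and SAP 4.8 requires changes to be approved before unblinding. What remains is that 5.5 authorises an adjustment in advance without stating its basis.

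Finally, neither document says that the percentage is held in the database. An adjustable cut implies that it is, but this needs confirming.

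**Conclusion.** The point holds in conditional form and is a low-severity improvement. As planned, the SAP's only efficacy use of tumor MET is a three-category subgroup, which does not match the stated aim of exploring MET as predictive. If benefit changes smoothly with staining, the split keeps about half to four fifths of the interaction information. That share is a steadier summary than a power figure, because it does not depend on the number of deaths or the effect size. The 8 to 19 points require a log-linear effect, a normal score, half High, MET known for 30% to 80% of deaths, and subgroup HRs averaging near 0.76. Other shapes give less, and a step at the cut reverses the comparison. None of the MET inputs is in the documents. Bias from adjusting the cut is a risk to be closed, not a finding.

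**What to change.** 1. In SAP 7.6, add for OS and PFS an exploratory stratified Cox model with treatment, MET staining percentage and their interaction. Fit it with a linear term and with a flexible form such as a restricted cubic spline. Show the fitted HR with its 95% CI across the MET range.
2. Keep the 50% split as a display and as a check for a step effect.
3. In SAP 5.5, state that any change to the cut uses only the pooled MET distribution, without outcome or treatment data, and is documented before unblinding under SAP 4.8.
4. Confirm that the laboratory transfers the percentage and not only the category. If it sends only the category, the percentage has to be requested.

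Cost: SAP wording and one extra exploratory analysis per endpoint. Sample size, alpha, visits and the primary analysis do not change. The downside is that a linear term is weaker than the split if the effect is a step, which is why both are kept.
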